Number and proportion of sputum samples (obtained at each scheduled visit and at each AECOPD visit) positive for bacterial pathogens (Hi and/or Mcat) will be computed together with exact 95% CIs by group and overall. The exact CIs will be estimated assuming independence of bacterial results across sputum samples.

The bacteriological vaccine efficacy outcome will be evaluated using same model as for clinical efficacy with the following SAS code:

```
PROC GENMOD data=<dataset>;
  CLASS trt age gold hexac country;
  MODEL nb_bact_exac = trt age gold hexac country
    / dist=NegBin LINK=log OFFSET=logfu;
RUN;
```

Where

nb_bact_exac are AECOPD associated to NTHi and/or Mcat by PCR method

As for the primary endpoint the number of bacterial associated AECOPD occurring from enrolment up to 1 month post-Dose 2 will be used as 'baseline' value. No difference between vaccine and placebo is expected in this period.

Descriptive statistics

For each treatment group, the total number of subjects, total number of AECOPD associated to NTHi and/or Mcat, total exposure time (in days), incidence of bacteriological associated exacerbation rate (per year and per each sub period considered) and the frequency of number of AECOPD will be tabulated.

The following statistics will be reported for AECOPD associated to NTHi and /or Mcat: N, mean, SD, median, Q1, Q3, min and max.

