6.6.1.2. Sputum bacterial/viral results via qPCR

[figure not shown]
Identification and quantification of the, *H. influenzae* (*Hi*), *M. catarrhalis* (*Mcat*) and *S. pneumoniae* (*Pn*) bacteria on frozen sputum samples will be performed using quantitative PCR (qPCR).

Testing results will be released as copies/mL values from 0 copies/mL up to the highest value.

Positivity cut-off (LOD – limit of detection): Samples with results below the positivity cut-off are negative. Samples with results equal to or above the LOD (equal to 1561, 927 and 1161 Copies/mL for *Hi*, *Mcat* and *Pn* respectively) are positive.

Limits of quantification (Lower (LLOQ) and Upper (ULOQ)): Only samples with results between the LLOQ and ULOQ are quantifiable. Nevertheless, as it is not needed to work with precise value, samples with results above the ULOQ and below LLOQ will be included in the quantitative analysis.

Figure 2 Sputum sample positivity by qPCR

For the occurrence, presence, acquisition and apparition analysis a sample will be considered positive (to *Hi*, or *Mcat* or *Pn*) if the qPCR results \geq LOD.

Load analysis will be performed for *Hi*, *Mcat* and *Pn* considering sputum samples with qPCR load above or equal to (\geq) the LOD, including the values belonging to the “not quantifiable” zone that will be anyway released by the assay (between LOD and LOQ, greater than ULOQ).

Occurrence and load of *Hi* and/or *Mcat*.

For each vaccine group the following analysis will be presented for sputum sample analysed via PCR:

CONFIDENTIAL

207489 (NTHI MCAT-002)

Statistical Analysis Plan Amendment 2 FDA Final Draft

- Overall proportion of sputum samples positive for Hi and Mcat with associated 95% CIs before vaccination (Day 1) and at any stable visit (Day 91, Day 181, Day 271, Day 361, Day 451) Day 91, Day 181, Day 271, Day 361, Day 451 and at any AECOPD visit
- Proportion of patients with sputum samples positive for Hi and Mcat with associated 95% confidence intervals (CIs), at each stable visit and at each AECOPD visit confirming acute exacerbation
- Summary statistics (N, mean, SD, median, minimum and maximum) and 95% CIs for the Hi and Mcat load will be displayed at each stable visit and at each AECOPD visit.

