For the overall proportion, estimate and confidence intervals will be computed using a Generalized Estimating Equations (GEE) model assuming a binomial distribution for the response variable with logit as link function and a compound symmetry correlation matrix (exchangeable structure) to account for the within-patient correlations [Liang, 1986] and the following SAS code will be applied for stable visits, AECOPD visits separately and for Hi and Mcat bacteria:

```

PROC GENMOD data=<dataset> descending;
CLASS pid trt;
BY bacteria;
MODEL sp_positive = trt / dist = bin LINK = logit lrci ;
REPEATED subject=pid/ type=exch PRINTMLE;
ODS OUTPUT ParameterEstimates=out_parm ClassLevels=Class;
RUN;

DATA result;
SET out_parm(where=(parameter='Intercept') drop=ChiSq ProbChiSq DF);
format percent LL UL percent8.1;
Percent=exp(estimate) / (1+exp(estimate));
LL=exp(LowerLRCL) / (1+exp(LowerLRCL));
UL=exp(UpperLRCL) / (1+exp(UpperLRCL));
unit=_N_;
RUN;

```

where:

pid: patient id

trt= treatment arm;

sp_positive=sputum sample positive to bacteria (Hi or Mcat)

Acquisition and apparition of Hi and Mcat

The following definitions will be used (see Section 11.2.7 for further details):

Acquisition: The first time a bacterium is detected in the sputum of a patient over the course of the study visits (a positive status at the visit considered as baseline excludes a subject from this analysis).

Apparition: Detection of a bacterium in the sputum of a patient taken during a study visit which was not detected in the sputum taken during the previous visit

CONFIDENTIAL

207489 (NTHI MCAT-002)

Statistical Analysis Plan Amendment 2 FDA Final Draft

The following analyses will be performed for Hi (alone or with other bacteria), Mcat (alone or with other bacteria) and either Hi or Mcat:

- Percentages of subjects with acquisition for each treatment group and risk ratio between groups, considering both Day 1 and Day 91 as baseline.
- Percentages of subjects with apparition for each treatment group and risk ratio between groups, considering Day 1 as baseline.
- Percentages of subjects with acquisition at AECOPD visit for each treatment group and risk ratio between groups, considering both Day 1 and Day 91 as baseline.
- Percentages of subjects with apparition at AECOPD visit (when negative at previous stable visit) for each treatment group and risk ratio between groups, considering Day 1 as baseline

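### The prescribed SAS code for the pooled proportion of Hi/Mcat-positive sputum samples reports an independence fit for one arm only, not the exchangeable GEE for each arm that the text specifies

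*SAP*

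**What the plan says.** Section 6.6.1.2 covers presence and load of Hi and Mcat by PCR. It opens with "For each vaccine group the following analysis will be presented for sputum sample analysed via PCR", so an estimate for each arm is required. For the overall proportion of positive samples it specifies a binomial GEE with logit link and "a compound symmetry correlation matrix (exchangeable structure) to account for the within-patient correlations". It then commits to a block of SAS code, to be run separately for stable and AECOPD visits and for each bacterium.

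The lines that matter are:

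- the model, "MODEL sp_positive = trt / dist = bin LINK = logit lrci", with `trt` also in the CLASS statement and `BY bacteria` as the only BY variable;
- the repeated statement, "REPEATED subject=pid/ type=exch PRINTMLE";
- the table saved, "ODS OUTPUT ParameterEstimates=out_parm ClassLevels=Class";
- the row kept, "SET out_parm(where=(parameter='Intercept') drop=ChiSq ProbChiSq DF", after which `LowerLRCL` and `UpperLRCL` are converted to percentages.

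Section 6.3.1.2 also plans CIs for proportions of positive samples: "The exact CIs will be estimated assuming independence of bacterial results across sputum samples".

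**The concern.** The text and the code describe different analyses, and the code is what will be run. Elsewhere the SAP offers code only as a pattern (the Kendall trend test in 6.3.1.1.2), but here the code itself is prescribed.

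Two things go wrong. The interval comes from a fit that treats several samples from one patient as unrelated, which is what the GEE was chosen to avoid. And one arm has no estimate. The missing arm would probably be noticed. The wrong interval might not be, because it would be labelled as GEE output and look plausible. Section 8 places presence and load by PCR in Priority 1, Step 2, so the result goes into the full clinical study report.

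**Working it through.** **Tracing the code**

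1. The REPEATED statement fits the exchangeable GEE. `PRINTMLE` additionally prints the starting maximum-likelihood fit, an ordinary logistic regression on all samples.
2. ODS OUTPUT saves `ParameterEstimates`, which holds that starting fit. No GEE estimates table is saved. The table contents are standard SAS behaviour, not SAP text, but the code confirms the reading: `lrci` and the LRCL variables are likelihood-ratio limits, these need a full likelihood, and a GEE has none.
3. `trt` is a CLASS effect in the model and BY splits on bacteria only. The intercept is therefore the logit for the reference level of `trt`. No later step computes the other arm.

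**Size of the interval error**

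The SAP gives no figure to reproduce and no within-patient correlation, so the correlation ρ is an assumption and a range is shown. The number of samples per patient, m, comes from 6.6.1.1: five stable visits after vaccination (Days 91, 181, 271, 361 and 451), or six if Day 1 is pooled with them. For AECOPD visits, m = 2 is an assumption.

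- Design effect: DE = 1 + (m − 1)ρ
- Saved width as a share of correct width: 1/√DE
- Actual coverage of a nominal 95% CI: 2Φ(1.96/√DE) − 1

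| m | ρ | DE | share of correct width | coverage |
|---|---|---|---|---|
| 5 | 0.1 | 1 + 4×0.1 = 1.4 | 85% | 90% |
| 5 | 0.2 | 1 + 4×0.2 = 1.8 | 75% | 86% |
| 5 | 0.4 | 1 + 4×0.4 = 2.6 | 62% | 78% |
| 5 | 0.6 | 1 + 4×0.6 = 3.4 | 54% | 71% |
| 6 | 0.2 | 1 + 5×0.2 = 2.0 | 71% | 83% |
| 6 | 0.6 | 1 + 5×0.6 = 4.0 | 50% | 67% |
| 2 | 0.2 | 1 + 1×0.2 = 1.2 | 91% | 93% |
| 2 | 0.6 | 1 + 1×0.6 = 1.6 | 79% | 88% |
| 1 | any | 1 | 100% | 95% |

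**Check by simulation**

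Setting: 300 subjects per arm, five samples each, 35% positive in the reference arm (assumed), 150 data sets per setting. The saved interval is the profile-likelihood CI of the independence fit.

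| ρ | saved CI: width, coverage | GEE robust CI: width, coverage |
|---|---|---|
| 0.1 | 4.8 points, 93% | 5.7 points, 97% |
| 0.3 | 4.8 points, 79% | 7.1 points, 95% |
| 0.5 | 4.8 points, 73% | 8.3 points, 95% |

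The Monte Carlo standard error of a coverage near 75% is √(0.75×0.25/150) ≈ 3.5 points, so these runs agree with the formula. The point estimate was the same from both fits (0.349 to 0.352); only the interval differs.

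**The case against.** The other side can say that this is a tertiary, within-group, descriptive proportion; that Section 7 calls all tertiary objectives exploratory; and that the negative binomial efficacy models do not use this code. All of that stands and limits the weight of the point. It can add that the input data set is an undefined placeholder and that a table with an empty column would be caught. That is fair for the missing arm. Running the code once per arm would cure it, as the BY-treatment rate code in 6.3.1.1.1 does, but the interval would remain wrong.

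A reader might infer more than the SAP supports:

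- **That the vaccine arm is the one lost.** Table 1 labels the arms 10-10-3-AS and PLACEBO, while 11.3 calls them VACCINE and PLACEBO. Under default ordering the last level differs between the two codings. One arm is missing; the SAP does not settle which.
- **That chance differences in carriage would look real.** No between-arm contrast of this proportion is planned. The acquisition and apparition risk ratios are subject-level and do not use this code.
- **That the culture analysis inherits the error.** Section 6.6.1.3 takes over the PCR method but displays proportions visit by visit, normally with one sample per patient, where independence does no harm.
- **That 6.3.1.2 contradicts the GEE.** Its exact CIs can be read as applying to each visit separately. The wording is ambiguous and needs clarifying, but a contradiction is not shown.
- **That the intervals are far too narrow everywhere.** The loss depends on the unknown correlation and on samples per patient. It is modest for two AECOPD samples and nil for one sample.

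**Conclusion.** The code is wrong as written. For the pooled-visit proportion it reports a CI that ignores clustering by patient, and it outputs only the reference-level arm although both are required.

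If the correlation is 0.2 to 0.6 and all five post-dose stable samples are obtained, the CI has about 75% to 54% of its correct width and covers about 86% to 71% instead of 95%. With two AECOPD samples per patient, coverage is about 93% to 88%. Fewer samples per patient or a lower correlation would reduce the loss. The primary and secondary efficacy conclusions are not affected. The point deserves correction because the stated method and the executed method differ, and the difference would be hard to see in the output.

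**What to change.** In 6.6.1.2, remove `LRCI` and `PRINTMLE` and do one of the following:

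- keep `trt` in the REPEATED model and obtain each arm's proportion with empirical (robust) limits through `LSMEANS trt / ILINK CL` or ESTIMATE statements; or
- run an intercept-only GEE `BY bacteria trt` and back-transform the intercept and its limits from `GEEEmpPEst`.

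Saving `GEEEmpPEst` from the present model is not enough. It gives an intercept and a treatment log-odds ratio, and the second arm's interval also needs their covariance.

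In 6.3.1.2, state that the exact independence CI applies only where each subject contributes one sample, and that any proportion pooled over visits uses the GEE.

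The cost is a few lines of code and a sentence of text, with no change to data collection. The downside is wider intervals for the pooled proportions: at five samples, about √1.8 = 1.34 to √3.4 = 1.84 times as wide over the assumed correlations.

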2. STUDY DESIGN

Figure 1 Study design overview

S = Screening Visit; V = Visit; PC = Phone contact; D = Day; FU = Follow-up; BS (1) = blood sample for humoral immunogenicity; BS (2) = blood sample for cell-mediated immunogenicity (CMI), this blood sample will only be collected from a sub-cohort of subjects; BS (3) blood sample for biomarkers; SP = sputum sample

The allowed maximum interval between Screening Visit and Visit 1 is 29 days. If a delay occurs for an eligible subject so that the interval exceeds 29 days, some study procedures performed during the Screening Visit needs to be repeated within 7 days (see Table 6 of the protocol for more details).

* An AECOPD visit should be scheduled as soon as possible after the onset of AECOPD symptoms (max 96 hours after and, if applicable, preferably before starting treatment with antibiotics) During this visit blood and sputum samples will be collected. In addition, follow-up phone call(s) and/or visit(s) will take place to determine the end of the AECOPD. These contacts will take place at least every 2 weeks until the AECOPD is resolved.

Investigational vaccine and placebo will be administered in addition to standard of care.

- **Experimental design:** Phase IIB, randomised, observer-blind, placebo-controlled, multi-centric study with two parallel groups.
- **Duration of the study:** for each subject enrolled, the study will last approximately 15 months from Visit 1 up to study completion (Visit 8).
 - Epoch 001: Screening Visit (Day -28 to Day -1).
 - Epoch 002 : Primary starting at Visit 1 (Day 1) and ending at Visit 8 (Day 451).
- **Primary completion Date (PCD):** Last Subject Last Visit (LSLV) from Visit 8 (Day 451) or last visit/contact of Epoch 002.
- **Study groups:**
 - **10-10-3-AS:** Approximately 300 subjects receiving two doses of the AS01_E-adjuvanted GSK Biologicals' NTHi-Mcat investigational vaccine containing 10 µg of PD, 10 µg of PE-PilA, and 3.3 µg of UspA2.
 - **CONTROL:** Approximately 300 subjects receiving two doses of placebo (PBS).

CONFIDENTIAL

207489 (NTHI MCAT-002)

Statistical Analysis Plan Amendment 2 FDA Final Draft

The following group names will be used for the statistical analysis

Table 1 Study groups and epochs foreseen in the study

Group order in tables	Number of subjects	Group label in tables	Group definition for footnote
1	~300	10-10-3-AS	2 doses of AS01E-adjuvanted NTHI/Mcat vaccine containing 10 mcg of PD, PE-PiA and 3 mcg of UspA2

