4.3. Tertiary endpoints**Sputum sample PCR:**

- Occurrence (presence and absence), bacterial load measured by PCR of NTHi and/or Mcat in sputum before first vaccination and at Day 91, Day 181, Day 271, Day 361 and Day 451 and at each AECOPD visit.
- Number of acquisitions and apparitions of NTHi and Mcat bacteria in sputum collected from Day 1 and from Day 91 and analysed by PCR.

Sputum sample culture:

- Occurrence (presence and absence), and semi-quantitative bacterial load measured in a subset of sputum sample by culture of NTHi and/or Mcat in sputum before first vaccination and at Day 91, Day 181, Day 271, Day 361 and Day 451 and at each AECOPD visit.

CONFIDENTIAL

207489 (NTHI MCAT-002)

Statistical Analysis Plan Amendment 2 FDA Final Draft

- Number of acquisitions and with apparitions of NTHi and Mcat bacteria in sputum collected from Day 1 and from Day 91 and analysed by culture.
- Rate of NTHi-associated and Mcat-associated, moderate and severe AECOPD.
- Rate of NTHi-associated and Mcat-associated any severity AECOPD.
- Rate of NTHi-associated and Mcat-associated AECOPD, by severity.
- Time to first moderate or severe NTHi-associated and/or Mcat-associated AECOPD.
- Time to first any NTHi-associated and rate Mcat-associated AECOPD.
- Time to first NTHi-associated and rate Mcat-associated AECOPD, by severity.
- Duration of each moderate and severe NTHi-associated and Mcat-associated AECOPD.
- Duration of NTHi-associated and/or Mcat-associated AECOPDs of any severity.
- Duration of NTHi-associated and/or Mcat-associated AECOPD, by severity.

QOL:

- Assessment of EXACT-PRO score, daily in the evening throughout the study, in all subjects.
- Assessment of CAT scores at Screening, Day 271 and Day 451, and from first vaccination to study conclusion for each AECOPD visit, in all subjects.
- Assessment of SGRQ-C score at Screening, Day 271 and Day 451, and from first vaccination to study conclusion for each AECOPD visit, in all subjects.
- Assessment of use of medication to treat (AE)COPD and healthcare utilization in all subjects throughout the study period.

Lung function:

- Assessment of FEV1% of predicted normal value at Screening, Day 271 and Day 451, in all subjects.

Biomarkers:

- Concentration of selected biomarkers (fibrinogen, hsCRP and IP-10), at Day 1 and Day 451, and for each AECOPD visit from first vaccination to study conclusion.

T helper profile:

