6.5.2.5. Concomitant Medication

This analysis will consider all medications taken (and reported) for different purpose than COPD or AECOPD. The analysis of medications to treat COPD or AECOPD (standard of care and not standard of care) is described in section 6.6.2.

Medications will be coded using the GSKDRUG dictionary.

The frequencies and percentages of subjects starting/reporting concomitant medications within the 7-day follow-up period (day 1 – day 7), during the 30-day follow-up period (day 1 – day 30) post-vaccination and during the entire study period will be tabulated by vaccine group for each study dose and across doses.

6.6. Other Analysis**6.6.1. Microbiological assessment****6.6.1.1. Sputum sample collection and quality**Sputum sample collection

Patient sputum sample will be collected (as stable visit) at Day 1 (before vaccination) and at Day 91, Day 181, Day 271, Day 361 and Day 451 and at each AECOPD driven visit, where AECOPD is confirmed.

Within each vaccine group the percentage of patients at each study visit (stable visit) and AECOPD confirmed visit will be computed overall and by the method (i.e., spontaneous at study visit or spontaneous at patient's home, induced using 0.9% saline or induced using 3% saline).

The proportion of sputum samples obtained at overall and at each stable and AECOPD visits and positive for specific bacterial pathogens by bacteriological culture and PCR will be computed, by vaccine group.

Sputum sample quality

The quality of sputum is assessed via squamous cells count, neutrophils cells count and bacteria direct smear. These will be summarized at any sputum visit (stable) and at any AECOPD confirmed visit, via frequencies tables (i.e., frequencies of sputum samples per quality scores [see section 11.2.7 in Annex 1] within each vaccine group)

CONFIDENTIAL

207489 (NTHI MCAT-002)

Statistical Analysis Plan Amendment 2 FDA Final Draft

If more than 20% of sputum samples have bad quality the analyses of bacteriological efficacy endpoint and bacteriological load (via PCR and culture) will be repeated in the subset of sputum samples with good and moderate quality.

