- Frequency table for apparition (number of apparitions for each subject from Day 1), by treatment groups.

Other bacteriological/viral pathogens

In addition to proportion of sputum positive to Hi (*Haemophilus influenza*) and Mcat (*Moraxella catarrhalis*) also the proportion of sputum samples obtained from PCR at pre-vaccination (Day 1), at Day 91, Day 181, Day 271, Day 361, Day 451 and at any AECOPD visit that are positive for specific bacteria (such as *S. pneumoniae*, *S. aureus*, *P. aeruginosa* and *Streptococcus pyogenes* [*S. pyogenes*]) and virus (such as *respiratory syncytial virus*, *parainfluenza virus*, *enterovirus/ rhinovirus*, *metapneumovirus*, *influenza virus*, *adenovirus*, *bocavirus* and *coronavirus*) will be presented together with the 95% CIs.

For the *S. pneumonia* and Rhinovirus summary statistics (N, mean, SD, median, minimum and maximum) and 95% CIs for the load will also be tabulated.

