7. ANALYSIS INTERPRETATION

The primary objective analysis (efficacy) of this study will be evaluated at alpha error of 13% (two-sided test) which is the measurement of the accuracy of our estimation.

Also 2-sided 95% CIs will be provided to show the precision of estimation.

For the secondary objectives we have the following:

- Inferential analyses for primary analysis of efficacy are planned to be performed at alpha level of 0.13 (two sided). No alpha adjustment for multiple testing in the secondary endpoints will be performed, and only the 2-sided 95% CIs will be provided
- All other efficacy and immunogenicity analyses are planned to be performed at alpha level of 0.05 with no adjustment for multiplicity.

CMI and safety analyses are intended to be descriptively only.

All tertiary objectives are exploratory and a p-value <0.1 is considered as reference for statistical significance in comparative analysis. Those comparisons should be interpreted with caution.

CONFIDENTIAL

207489 (NTHI MCAT-002)

Statistical Analysis Plan Amendment 2 FDA Final Draft

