Mean, median	Number of decimals in the raw data + 1
SD	Number of decimals in the raw data + 2
Minimum, maximum, range	Number of decimals in the raw data

LL = Lower Limit UL = Upper Limit CI = Confidence Interval

SD = Standard deviation

CONFIDENTIAL207489 (NTHI MCAT-002)
Statistical Analysis Plan Amendment 2 FDA Final Draft**11.2.7. Other endpoints****Acquisition and apparition of NTHi and Mcat**

For the purpose of the analysis the following definitions are to be used:

1. Acquisition: the first time a bacterium is detected in the sputum of a patient over the course of study visits (bacterium presence at first study visit is not considered acquisition); either stable or exacerbation visits are considered.
2. Apparition: detection of a bacterium in the sputum of a patient taken during a study visit which was not detected in the sputum taken during the previous visit; either stable or exacerbation visits are considered.
3. No acquisition: a visit at which a bacterium is not detected in the sputum or a visit that follows an acquisition; first study visit is not considered. either stable or exacerbation visits are considered.
4. No apparition: a visit at which a bacterium is not detected in the sputum or a visit at which a bacterium is detected but not preceded by a negative visit

Note: in qPCR acquisition and apparition a bacterium detected means the qPCR results \geq LOD.

Sputum quality criteria

Quality of sputum is define using the following criteria and based on squamous cells count in fresh sputum [Geckler, 1977]:

- >25 squamous epithelial cells/field \rightarrow sample of bad quality
- $10-25$ squamous epithelial cells/field \rightarrow sample of moderate quality
- < 10 squamous epithelial cells/field \rightarrow sample of good quality

Computation of the final HRV status

The final HRV status takes into account data coming from both the Allplex assay and HRV RT-qPCR assay. A new variable for the final postivitiy/negativity (qualitative results) of HRV, for each sample, will be computed based on the below combination:

CONFIDENTIAL

207489 (NTHI MCAT-002)
 Statistical Analysis Plan Amendment 2 FDA Final Draft

Allplex HRV result	Allplex HEV result	HRV RT-qPCR	Final HRV result (variable to be created)
POSITIVE	NEGATIVE	Any results	POSITIVE
	POSITIVE	Any results	
NEGATIVE	POSITIVE	IR	NEGATIVE
		NFR	
		RBSA	
		< LOD	
	POSITIVE	≥ LOD	POSITIVE
	NEGATIVE	Not tested	NEGATIVE

HRV= Human Rhino-Virus

HEV= Human Enter-Virus

IR = Invalid Result

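### Apparition is defined as a number that can recur, but the arms are compared only on the percentage of subjects with at least one; the count has no between-arm estimate

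*SAP*

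**What the plan says.** All references are to SAP Amendment 2.

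- **Endpoint, section 4.3.** For PCR: "Number of acquisitions and apparitions of NTHi and Mcat bacteria in sputum collected from Day 1 and from Day 91 and analysed by PCR". For culture: "Number of acquisitions and with apparitions of NTHi and Mcat bacteria in sputum collected from Day 1 and from Day 91 and analysed by culture".
- **Definition, section 11.2.7.** Apparition is "detection of a bacterium in the sputum of a patient taken during a study visit which was not detected in the sputum" at the previous visit. Stable and exacerbation visits both count.
- **Sampling after Day 1, section 6.6.1.1.** Sputum is collected at "Day 91, Day 181, Day 271, Day 361 and Day 451 and at each AECOPD driven visit, where AECOPD is confirmed".
- **Between-arm analysis, sections 6.6.1.2 (PCR) and 6.6.1.3 (culture).** "Percentages of subjects with apparition for each treatment group and risk ratio between groups, considering Day 1 as baseline". A parallel line gives the percentage and risk ratio for apparition at AECOPD visits.
- **Use made of the count, same sections.** "Frequency table for apparition (number of apparitions for each subject from Day 1), by treatment groups".
- **Status, section 7.** "All tertiary objectives are exploratory and a p-value <0.1 is considered as reference for statistical significance in comparative analysis".

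**The concern.** The endpoint is worded as a number, and its definition allows several apparitions per subject, but the only between-arm effect measure is yes or no per subject. A subject with three apparitions counts the same as a subject with one. The table of counts shows the repeats but gives no estimate of the treatment effect on them and no measure of its precision.

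Nor does the percentage allow for opportunity. For acquisition, section 6.6.1.2 excludes subjects who are positive at baseline. No comparable rule is given for apparition, so a subject with two samples before withdrawal sits in the denominator like one sampled at every visit.

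At stake is an exploratory reading of whether the vaccine reduces new detections. The comparison may be less sensitive than the data allow, and the stated endpoint is left without an effect estimate. Acquisition is not affected: it can happen only once per subject, so a percentage suits it.

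**Working it through.** **Can apparition recur?** There are five stable visits after Day 1. For a subject negative at Day 1, the pattern positive, negative, positive, negative, positive over Days 91 to 451 gives three apparitions. AECOPD visits can add more.

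**Is there a plan figure to reproduce?** No. The SAP states no power, rate or sample size for apparition, so every rate below is assumed. From the plan come about 300 subjects per arm (section 2: "Approximately 300 subjects receiving two doses of placebo (PBS" for the control group), 1:1 allocation (section 11.3) and the 0.10 reference level (section 7), taken here as two-sided.

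**Analytic check.** Let control subjects have a mean of μ apparitions with negative binomial dispersion k, and let the true rate ratio be 0.70.

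- Probability of at least one: 1 − (1 + kμ)^(−1/k).
- Variance of the log rate ratio: [(1/μ₀ + k) + (1/μ₁ + k)] / 300.

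Worked case, μ₀ = 0.5, k = 0.5, so μ₁ = 0.35:

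- Control: 1 − 1.25^(−2) = 0.360. Vaccine: 1 − 1.175^(−2) = 0.276. Risk ratio 0.766; power 72% by a two-proportion test.
- Count: variance (2.5 + 3.357)/300 = 0.01952, SE 0.1397. |log 0.70|/SE = 0.3567/0.1397 = 2.55, and 2.55 − 1.645 = 0.91, so power is 82%.

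With μ₀ = 0.3 and k = 0 (Poisson) the figures are 66% and 70%. Larger μ and k give gains of up to 24 points, but this formula puts no ceiling on the count, whereas the visit schedule does. The simulation is the better guide.

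**Simulation.** Two-state (negative/positive) model, 300 per arm, five post-baseline stable visits, a mean of one AECOPD visit, 10% dropout and 30% positive at Day 1. The vaccine lowers new detection by 30%; 2,000 trials per row. The count analysis is a rate per post-baseline sample with robust variance. Power is at two-sided 0.10.

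| New detection / clearance per visit | Subjects vary in risk | Control apparitions that are repeats | Power, % of subjects | Power, rate per sample | Gain (points) |
|---|---|---|---|---|---|
| 0.1 / 0.5 | no | 10% | 83.8% | 87.6% | 3.8 |
| 0.1 / 0.5 | yes | 20% | 67.6% | 78.8% | 11.2 |
| 0.2 / 0.5 | no | 20% | 94.7% | 98.4% | 3.7 |
| 0.2 / 0.5 | yes | 29% | 79.8% | 91.0% | 11.2 |
| 0.3 / 0.6 | no | 30% | 97.5% | 99.8% | 2.3 |
| 0.3 / 0.6 | yes | 37% | 83.4% | 95.8% | 12.4 |
| 0.2 / 0.3 | no | 15% | 93.2% | 97.1% | 3.9 |
| 0.2 / 0.3 | yes | 22% | 74.6% | 85.4% | 10.8 |

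With no vaccine effect, both methods rejected in about 10% of trials. The small gains in rows already near 95% partly reflect the ceiling at 100%.

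**Other assumed settings.** Further runs at 0.10 used the rate per at-risk pair (earlier sample negative). One set, with true clearance, gave gains of about 0 to 8 points. When persistent carriers fluctuate around the detection limit, the change ranged from −3 to +9 points.

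**Unequal sampling.** If the vaccine reduced AECOPD visits from 1.3 to 1.0 per subject with no effect on detection, the percentages were 57.7% (control) and 56.4% (vaccine). That is a ratio of 0.564/0.577 = 0.98, with rejection still at 9.9%. A wider gap, 1.5 against 1.05 AECOPD samples with 250 per arm, moved the ratio to 0.96–0.97 and rejection to 11–14%. The distortion is modest.

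**The case against.** **The endpoint phrase is loose.** It covers acquisition and apparition together, and for acquisition a number can only mean a number of subjects. That is fair, but the planned table of apparitions per subject shows that the count was in mind.

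**Repeats are reported.** A reader might infer that repeat apparitions are thrown away. The documents do not support that: they are tabulated by arm for both PCR and culture, and are missing only from the comparison.

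**A risk ratio is not a biased rate ratio.** In the analytic runs a rate ratio of 0.70 corresponds to a risk ratio of 0.73 to 0.84. One might call this dilution, but the two are different estimands. The percentage of subjects is a legitimate, readable measure.

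**Repeats may not be new detections.** Section 11.2.7 needs only a crossing of the PCR limit of detection, without strain confirmation. A carrier near that limit generates repeats that a count model weights fully, and the advantage can then vanish. This stands.

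**The at-risk denominator has its own problems.** It looks like the natural offset, but its log is undefined for a subject with no negative earlier sample. It is also a post-randomisation quantity that the vaccine may alter through detection, clearance or AECOPD frequency. This stands, and rules it out as the main offset.

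**Repeat bacterial data are modelled elsewhere.** Section 6.6.1.2 fits a GEE to repeated sputum positivity, and section 6.3.1.2 counts every associated AECOPD in a negative binomial model. True, but neither estimates an effect on apparition.

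**Conclusion.** The mismatch stands on the text. A count endpoint that can recur receives a between-arm estimate only in yes/no form, and the count has no effect measure, confidence interval or allowance for samples taken. This applies equally to PCR and culture.

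The cost is uncertain. In the main simulation the loss was about 2 to 4 points where subjects had equal risk and 11 to 12 points where risk varied. Over all assumed settings it runs from negligible, when repeats are rare or mostly fluctuation around the detection limit, to roughly 5 to 15 points in several settings with frequent true repeats. These figures assume about 300 evaluable subjects per arm. Culture covers only about half the subjects (section 6.3.1.3), and its absolute power would be lower.

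A stronger reading, that the planned percentage analysis is wrong or should be replaced, is not supported. The endpoint is tertiary and exploratory, the plan sets no power target for it, and the primary conclusion is unaffected. This is an optional improvement.

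**What to change.** In sections 6.6.1.2 and 6.6.1.3, **add and do not substitute** a negative binomial model, or a Poisson model with robust variance, for the number of apparitions per subject. Use treatment and the primary-model covariates (age group, GOLD grade, exacerbation history, country), with the log number of evaluable post-baseline sputum samples as offset. Report the rate ratio with 95% CI. Subjects without any such sample cannot contribute. This offset also depends on AECOPD visits, but not on the detection results themselves.

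Keep the percentages, risk ratios and frequency table as planned. Present the rate per at-risk pair only as a supportive result, stating that subjects with no at-risk pair drop out and that the denominator is post-randomisation.

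The cost is SAP wording and a small adaptation of the existing GENMOD code. The counts are already needed for the frequency table, and no new data are required. The downside is one more exploratory comparison without multiplicity adjustment.
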